**Appendix J. Child-Pugh Score for Subjects with Liver Impairment**

Measure	1 point	2 points	3 points
Total bilirubin, $\mu\text{mol/L}$ (mg/dL)	<34 (<2)	34-50 (2-3)	>50 (>3)
Serum albumin, g/L (g/dL)	>35 (>3.5)	28-35 (2.8-3.5)	<28 (<2.8)
PT/INR	<1.7	1.71-2.30	>2.30
Ascites	None	Mild	Moderate to Severe
Hepatic encephalopathy	None	Grade I-II (or suppressed with medication)	Grade III-IV (or refractory)

Points	Class
5-6	A
7-9	B
10-15	C

IGHV	immunoglobulin heavy-chain variable region
IRC	independent review committee
IRR	infusion related reaction
ITT	intent-to treat
IWCLL	International Workshop on Chronic Lymphocytic Leukemia Criteria
IWRS	Interactive Web Response System
MedDRA	Medical Dictionary for Regulatory Activities
MRU	medical resource utilization
NCI	National Cancer Institute
NE	not evaluable
NED	no evidence of disease
nPR	nodular partial response
ORR	overall response rate
OS	overall survival

Abbreviation	Definition
PD	progressive disease
PFS	progression-free survival
PK	Pharmacokinetic
PR	partial response
PRO	patient reported outcome.
PT	preferred term
SAE	serious adverse event
SAP	statistical analysis plan
SD	stable disease
SLL	small lymphocytic lymphoma
SOC	system organ class
TEAE	treatment-emergent adverse events
WBC	white blood cell count
WHO	World Health Organization

1. INTRODUCTION

This statistical analysis plan (SAP) lays out key elements including definitions and statistical methods for analysis of data in evaluation of efficacy and safety for the PCYC-1130-CA study. Analyses of pharmacokinetics (PK) data and exploratory analyses for clonal evolution, disease-related mechanisms of resistance and the secreted protein analysis for obinutuzumab-related infusion reactions will be addressed in separate documents.

Throughout this SAP, “study treatment” and “study drug” are used interchangeably.

1.1. Study Design

This is a randomized, multicenter, open-label, Phase 3 study designed to evaluate the safety and efficacy of ibrutinib in combination with obinutuzumab, when compared to chlorambucil in combination with obinutuzumab, in subjects diagnosed with CLL or SLL, who are treatment-naïve but now require therapy.

Subject participation includes a Screening Phase, a Pre- Progressive Disease (Pre-PD) Phase, and a Follow-up Phase.

The Screening Phase is up to 30 days prior to randomization. The Pre-PD Phase extends from randomization until disease progression (PD), death, loss to follow up, or consent withdrawal, whichever occurs first. During this phase, subjects receive the study treatment once randomized and the response evaluations are scheduled every 4 cycles from the initial dose of study drug until Cycle 33, and then every 6 cycles until disease progression regardless of whether subject is on study treatment or has discontinued study treatment due to a reason other than PD. The Follow-up Phase begins once a subject has progressive disease and continues until death, loss to follow up, consent withdrawal, or study end, whichever occurs first.

The response and progression evaluations are performed in accordance with the IWCLL guidelines including recent clarifications (Hallek 2008, Hallek 2012, Hallek 2013, Cheson 2012, and IWCLL 2017). An independent review committee (IRC) was established to conduct progression and response assessment centrally. Criteria for response categories, as well as the process and convention of the IRC were prospectively detailed in the IRC charter.

An independent Data Monitoring Committee (DMC) is formed and constituted according to regulatory agency guidelines. Detailed information regarding the composition of the DMC and detailed DMC procedures are provided in a separate charter. The DMC reviews the safety data periodically and provides recommendations according to the charter.

Study Dosage and Administration

Treatment Arm A: Ibrutinib PO and Obinutuzumab IV

Ibrutinib will be given orally at a dose of 420 mg daily (3 capsules) until disease progression or unacceptable toxicity.

Obinutuzumab will be administered intravenous at a fixed dose of 1000 mg over 6 cycles: given on Days 1+2 (100 mg on Day 1 and 900 mg on Day 2), Day 8 (1000 mg) and Day 15 (1000 mg) of Cycle 1 and on Day 1 (1000 mg) only of subsequent cycles, for up to 6 cycles.

Treatment Arm B: Chlorambucil PO and Obinutuzumab IV for Six 28-day Cycles

Chlorambucil will be administered orally at a dose of 0.5 mg/kg body weight, on Days 1 and 15 of each cycle, for up to 6 cycles.

Obinutuzumab will be administered the same as in arm A.

Upon IRC-confirmed progression, subjects in Arm B have the opportunity to receive ibrutinib monotherapy orally at a dose of 420 mg daily (3 capsules) continuously until determined otherwise by the investigator.

1.2. Endpoints

1.2.1. Primary Endpoint

- Progression free survival (PFS) by IRC

1.2.2. Secondary Endpoints

- PFS by IRC in high risk analysis set
- Rate of sustained hemoglobin improvement
- Rate of MRD-negative response
- ORR by IRC
- OS
- Rate of infusion related reactions
- Rate of sustained platelet improvement
- Rate of clinically meaningful improvement in EQ-5D-5L utility score

1.2.3. Safety Assessments

- Safety and tolerability of ibrutinib in combination with obinutuzumab compared with chlorambucil in combination with obinutuzumab

1.3. Statistical Hypotheses

The primary hypothesis of this study is that the experimental treatment ibrutinib + obinutuzumab compared with chlorambucil + obinutuzumab will significantly improve PFS in subjects diagnosed with CLL or SLL who are treatment-naive but now require active therapy.

The statistical hypotheses are as follows:

H_0 : The PFS distributions of experimental treatment group, $S_I(t)$, and the control group, $S_C(t)$, are equal at all time points t :

$$S_I(t) = S_C(t), \text{ for all } t > 0$$

versus

H_1 : The PFS distributions of experimental treatment group, $S_I(t)$, are different from the control group, $S_C(t)$, at at least one time point t :

$$S_I(t) \neq S_C(t), \text{ for some } t > 0$$

These hypotheses will be tested using a 2-sided stratified log-rank test at α level of 0.05.

1.4. Sample Size Determination

This study was powered for testing the primary hypothesis of this study.

The sample size is calculated based on the assumptions:

- Randomization ratio of 1:1
- Median PFS of 27 months for Arm B (chlorambucil in combination with obinutuzumab)
- Target hazard ratio of 0.55, which corresponds to median PFS of 49.1 months for Arm A (ibrutinib combined with obinutuzumab).

On this basis, 94 PFS events provide 80% power to achieve a statistical significance level of 5% (2-sided) under exponential distribution. With an estimated accrual rate of 18 subjects per month, approximately 212 eligible subjects were to be enrolled to observe 94 PFS events in about 36 months from the first subject randomized.

The sample size and power calculations were calculated using the software package, East (Cytel Software Corp, Cambridge, MA) version 6.3.

1.5. Planned Analysis

1.5.1. Interim Analysis

No interim analysis is performed in this study.

1.5.2. Primary Analysis

The primary analysis of PFS will be performed after approximately 94 confirmed progression/death events have occurred. The analysis of the secondary endpoints including OS will be performed at the time of PFS primary analysis.

1.5.3. Final Analysis

After the primary analysis of PFS, the Sponsor will continue to follow the subjects for approximately 4 years after the first subject was enrolled. When the study closed, a final analysis will be performed, and a CSR addendum will be drafted.

1.6. Testing Procedure and Level of Significance

To preserve the study wise type I error rate of 0.05, the primary and secondary endpoints will be tested based on a serial gatekeeping testing procedure at the two-sided significance level of 0.05 according to the hierarchical order as listed in 1.2.2.

1.7. Blinding and Randomization Methods

1.7.1. Blinding Method

In this open-label study, neither the subjects nor the investigators are blinded to treatment. However, access to efficacy data is controlled so that the Sponsor's staff overseeing the conduct of the study or analyzing/summarizing data do not have an aggregated efficacy summary by treatment arm prior to database lock. Details are described in the Minimizing Bias Document.

Assessment for progression and response assessment is performed centrally by the IRC. Members of the IRC are blinded to the study treatment. The IRC data flow and workflow are detailed in the IRC charter.

1.7.2. Randomization Method

Central randomization will be implemented in this study. Two randomization schemes will be generated: one for each geographic region (North America versus Rest of World). Under each scheme, subjects will be randomized based on the following stratification factors:

- ECOG 0-1 vs 2
- Cytogenetics - will be stratified into one of three categories
 1. del 17p
 2. del 11q without del 17p
 3. others (neither del 17p nor del 11q)

Subjects will be randomized in a 1:1 ratio to either Treatment Arm A or Treatment Arm B within each randomization stratum. This randomization scheme will be implemented within the Interactive Web Response System (IWRS).

2. GENERAL ANALYSIS CONSIDERATION

2.1. Analysis Sets

Intent-To-Treat (ITT) population: defined as all subjects who were randomized. Subjects will be grouped according to the treatment assigned at randomization. This population will be the primary population for the analyses of efficacy endpoints, disposition, demographics and baseline characteristics, baseline disease characteristics, subsequent anticancer therapy and patient-reported outcome data.

Safety population: defined as all subjects who received at least 1 dose of any one of the three study drugs (ibrutinib, chlorambucil, or obinutuzumab). Safety data will be analyzed as treated. The Safety Population will be used to summarize the safety (including dosing and concomitant medications) data.

High risk analysis set: defined as randomized subjects with del17p or TP53 mutation or del 11q at baseline per central lab results.

2.2. Definition of Subgroups

Subgroup analyses will be performed for the selected variables to assess the internal consistency of the treatment benefit.

3. SUBJECT INFORMATION

Subject information will be summarized descriptively. No inferential test will be performed.

3.1. Subject Disposition

Subject randomization will be summarized by region, country, site and by stratification factors. Subject disposition for each study treatment and for study participation will be tabulated. The overall duration of receiving any study treatment and time on study will be summarized correspondingly.

Time on study is defined in the same way as overall survival with reversed censoring, i.e., subjects who died will be censored at death date. The Kaplan-Meier method will be used to estimate the median time on study.

3.2. Demographics and Baseline Characteristics

Demographic information and baseline characteristics including but not limit to age, gender, race, histology type, time from initial diagnosis, staging, and potential prognostic factors will be summarized with descriptive statistics for ITT population by treatment arm and, in addition, by subgroups.

3.3. Prior and Concomitant Medications

Medications will be coded to preferred term and Anatomical Therapeutic Chemical (ATC) class according to World Health Organization (WHO) Drug dictionary.

Prior medications are defined as medications that started prior to the first dose date of study drug. Concomitant medications are defined as medications that were taken at any time on treatment (i.e. from the date of the first dose of study drug through the date of the last dose of study drug).

Concomitant medications will be summarized by therapeutic class and preferred term in the safety population. The following concomitant medications of special interest will be summarized separately: growth factors, blood supportive products and immunoglobulin, CYP3A inhibitors/inducers, anticoagulants and/or antiplatelet.

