## 6. CONCOMITANT MEDICATIONS/PROCEDURES

Concomitant therapies must be recorded from the time of ICF signing until 30 days after the last dose of study drug.

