##### **7.1.1.4. Prior and Concomitant Medications**

All medications from the signing of ICF through 30 days after the last dose of study drug will be documented. After a subject discontinues study treatment, receipt of all subsequent anticancer therapies will be collected until death, subject withdrawal of full consent, loss to follow-up, or study termination by Sponsor, whichever comes first.

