5. SAFETY ASSESSMENTS

Safety data will be summarized for the safety population. Table 2 summarizes the safety analyses to be performed.

Adverse events will be coded in accordance with the MedDRA. Severity of AEs will be graded by the investigator according to the NCI-CTCAE v4.03 for non-hematological AEs and IWCLL 2008 guidelines for hematologic toxicity.

Treatment-emergent period is defined as the period from the date of the first dose of study treatment up to 30 days after the date of the last dose of study treatment or the day before initiation of subsequent antineoplastic therapy (including the cross-over ibrutinib monotherapy for arm B subjects), whichever comes first.

The treatment-emergent adverse events (TEAE) are those events that occur or worsen during the treatment-emergent period or that are related to the study treatment. Unless otherwise specified, only TEAEs will be included in the adverse event summaries.

All laboratory values will be converted to and reported as international standard (SI) units. In general, only data from the central laboratory will be summarized and analyzed. Hematologic parameters including platelet counts, hemoglobin, and neutrophils will be assessed by the grading scale for hematologic toxicity in CLL studies in the IWCLL 2008 guidelines. All other gradable laboratory parameters will be graded using the NCI CTCAE v4.03. Unless otherwise specified, only baseline and post-baseline values collected during the treatment-emergent period will be included in the safety analysis.

Table 2: Summary of Safety Assessments

Assessment Type	Definition	Analysis Methods
AE	TEAEs, SAEs, Grade 3 or worse TEAEs, related TEAEs, TEAEs leading to treatment discontinuation, TEAEs leading to dose reduction, TEAEs leading to death, protocol-defined events of special interest and other safety observations. TEAEs within the first 9 months of study treatment and TEAEs in the crossover period	Descriptive summary statistics and/or listings
Lab	Worst post-baseline toxicity grade for selected CTCAE gradable hematology and chemistry. Abnormalities in creatinine clearance, uric acid, and liver function	Descriptive summary statistics and/or listings
Vital Signs and other Observations Related to Safety	Blood pressure, heart rate, new or worsened eye-related symptoms	Descriptive summary statistics and/or listings

TEAE= treatment-emergent adverse event; SAE= serious adverse event; CTCAE= Common Terminology Criteria for Adverse Events.

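### SAP 3.3 closes the concomitant-medication window at the last dose of study drug, so growth factors and blood products first given in the next 30 days are recorded but not summarized, although adverse events in those days are counted

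*SAP*

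**What the plan says.** SAP 3.3 (Prior and Concomitant Medications) gives the definition: "Concomitant medications are defined as medications that were taken at any time on treatment", which it then spells out as "from the date of the first dose of study drug through the date of the last dose of study drug". The same section makes a separate summary of special-interest concomitant medications, beginning with "growth factors, blood supportive products and immunoglobulin". No other window is given for that summary, so it uses the same one.

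Data collection runs longer. Protocol section 6 states: "Concomitant therapies must be recorded from the time of ICF signing until 30 days after the last dose of study drug". Protocol 7.1.1.4 repeats it: "All medications from the signing of ICF through 30 days after the last dose of study drug will be documented".

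The adverse event window also runs longer. SAP section 5 (Safety Assessments) carries the treatment-emergent period "up to 30 days after the date of the last dose of study treatment or the day before initiation of subsequent antineoplastic therapy", whichever comes first, and counts cross-over ibrutinib in Arm B as such therapy.

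**The concern.** Three windows bear on the same events, and one of them is 30 days shorter with no reason given. The SAP 3.3 special-interest summary shows hematologic support, and the cytopenias that prompt such support are counted over the longer window. Protocol 5.3.3.4 describes the common chlorambucil toxicities as hematologic, and protocol 1.3.3 lists late-onset and prolonged neutropenia among the important obinutuzumab risks. The days just after the last dose are therefore days in which support may be needed.

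Dose holds can produce the same gap. The protocol allows study drugs to be held for toxicity for up to 28 days before discontinuation (5.3.1.4, 5.3.2.4, 5.3.3.3). If every drug is held and none is restarted, the last-dose date is the day before or at the start of the hold, and support first given during the hold falls outside SAP 3.3.

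At stake is the completeness of one descriptive safety table and its agreement with the adverse event tables in the same report.

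**Working it through.** The plan states no figure to reproduce here, so the check compares windows by day count, with first dose as day 1 and 28-day cycles.

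**Windows, in days after the last dose of the last study drug**

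| Purpose | Source | Days after last dose |
|---|---|---|
| Recording medications | Protocol 6 and 7.1.1.4 | 30 |
| Counting adverse events | SAP 5 | 30, or to the day before subsequent antineoplastic therapy |
| Tabulating medications | SAP 3.3 | 0 |

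I read study drug in SAP 3.3 as the whole randomized regimen, so the window closes at the last dose of whichever drug ends last. The SAP introduction uses study drug and study treatment interchangeably, and protocol 10.8.1 refers to the last dose of the last study drug.

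**Arm B, full course on schedule**

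- The last dose is chlorambucil on Cycle 6 Day 15: 5 × 28 + 15 = day 155.
- The treatment-emergent window ends at 155 + 30 = day 185.
- Outside SAP 3.3: 30 / 185 = 16.2% of treatment-emergent days.

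**Arm B, chlorambucil stopped early and obinutuzumab completed**

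Protocol 5.3.2.6 continues obinutuzumab to six cycles, so its last dose is Cycle 6 Day 1: 5 × 28 + 1 = day 141. Of the 30 days after the last chlorambucil dose, the number still inside the SAP 3.3 window is min(30, 141 − day of last chlorambucil dose):

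| Last chlorambucil dose | Day | Days inside, of 30 |
|---|---|---|
| Cycle 4 Day 15 or earlier | 99 or earlier | 30 |
| Cycle 5 Day 1 | 113 | 28 |
| Cycle 5 Day 15 | 127 | 14 |
| Cycle 6 Day 1 | 141 | 0 |

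The 30-day gap then opens after day 141 instead, and is 30 / (141 + 30) = 17.5% of treatment-emergent days.

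**Arm A**

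The gap opens only when all drug stops. Time on ibrutinib is open-ended, so these durations are assumptions:

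- 12 months (365 days): 30 / 395 = 7.6%
- 36 months (1,096 days): 30 / 1,126 = 2.7%
- 49.1 months (1,494 days): 30 / 1,524 = 2.0%

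**Either arm, all drug stopped at once after Cycle 2 Day 1**

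The last dose is on day 29 and the window ends on day 59, so 30 / 59 = 51% of treatment-emergent days are outside. This requires both drugs to end together.

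All of these are shares of treatment-emergent days. They are not shares of recorded days, because recording starts at consent. With a full 30-day screening period the Arm B figure against recorded days would be 30 / (185 + 30) = 14%.

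**The case against.** SAP 3.3 deliberately defines concomitant as on treatment, and collecting data for longer than one table uses them is not a contradiction. That is fair: this is a gap in coverage, not an error in the definition. The SAP nevertheless gives no reason for using a shorter window than it uses for the events being treated.

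A reader might infer that support for any toxicity that ends treatment is left out. The documents do not support that. A medication taken on or before the last-dose date counts even if it continues, and when one drug is stopped the other continues (protocol 5.2.1, 5.2.2, 5.3.2.6). Only support first given after the last dose of the last drug is missed.

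A reader might also take 16% as the understatement of support use in Arm B. It is a share of days. If the table counts subjects by preferred term, anyone already given the same product on treatment is already in it. The documents give no basis for estimating how many first uses fall in the gap.

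Nor is the difference between arms a product of this rule. Arm B's window ends early because its treatment does. After the fix, Arm B would close at day 185 while Arm A subjects still on ibrutinib stay open, and the adverse event window has the same asymmetry.

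The strongest objection is that the protocol has another measure. Medical resource utilization covers transfusions and growth-factor use (7.1.1.12, 10.7.3.5). It is collected at Cycle 7 Day 1 (6 × 28 + 1 = day 169, inside Arm B's missing 30 days) and at the End-of-Treatment visit. This softens the point, since these uses are captured. It does not remove it: protocol 10.7.3 defers the details to the SAP, and the SAP text lists MRU as an abbreviation, specifies no analysis of it, and does not name it among the analyses left to separate documents.

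**Conclusion.** The point holds as a minor inconsistency in a descriptive table. Growth factors and blood products first given in the 30 days after the last dose of the last study drug are recorded but fall outside the SAP 3.3 summaries, even when the cytopenia being treated is tabulated as treatment-emergent. For an Arm B subject finishing on schedule with no earlier antineoplastic therapy, that is 30 of 185 treatment-emergent days (16%). The effect on reported support use is unknown and may be small.

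The conclusion assumes on-schedule 28-day cycles and that the window closes with the last drug of the regimen. The adverse events and the laboratory grades for those days are still reported under SAP section 5, so the toxicity itself is not hidden. The primary endpoint, alpha and power are untouched.

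**What to change.** In SAP 3.3, define the concomitant-medication window as first dose to the end of the treatment-emergent period in SAP section 5, at least for the growth-factor and blood-product summaries. The existing cut at subsequent antineoplastic therapy, including cross-over ibrutinib, keeps later-line support out of the table. It would help to state in the same sentence that the window runs to the last dose of the last study drug.

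The cost is one SAP sentence and the corresponding table programming. The data are already collected, so no procedure or visit changes. The only downside is that reported support use may rise slightly.

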3.4. Extent of Exposure to Study Treatment

Exposure to ibrutinib, chlorambucil, obinutuzumab will be summarized separately for treatment duration and dosing information (e.g. total cumulative dose administered, relative dose intensity, ibrutinib or chlorambucil dose reduction due to adverse events).

3.5. Subsequent Antineoplastic Therapies

Subsequent CLL/SLL antineoplastic agents will be summarized by type of therapies.

4. ANALYSIS FOR ENDPOINTS

Analysis of endpoints will be conducted on the ITT population, unless otherwise specified. Table 1 summarizes the efficacy endpoints and analysis methods to be performed.

The following two randomization stratification factors will be used for the stratified analysis/test: ECOG performance status (0, 1 versus 2) and Cytogenetics (del 17p, del 11q without del 17p, others). To reflect the randomization process and maintain the integrity of randomization, all stratified tests will be based on randomization stratification factors as recorded in the IWRS.

For subgroup and exploratory analysis, only the analysis that provide meaningful information will be presented.

Table 1: Definitions and Analyses for Endpoints

Endpoint	Definition	Analysis Method
Primary Endpoint		
PFS assessed by IRC	Time from the date of randomization to the date of IRC-assessed disease progression or date of death from any cause, whichever occurred first, regardless of the use of subsequent antineoplastic therapy prior to documented PD or death.	
Primary Treatment effect of ibrutinib plus obinutuzumab compared to chlorambucil plus obinutuzumab was tested with a log-rank test. The hazard ratio and its 95% CI based on a Cox regression model are calculated. PFS distribution is estimated by Kaplan-Meier method: median PFS and landmark estimates with 2-sided 95% CIs are to be provided for each treatment arm.
 
Sensitivity Analyzing PFS assessed by investigator using the same method as PFS assessed by IRC.
 
Subgroup Hazard ratio and its 95% CI based on unstratified Cox regression model for each subgroup.

Secondary Endpoints		
PFS assessed by IRC in high risk analysis set	Defined the same as the primary endpoint.	Analyzed the same as primary endpoint in high risk analysis set
ORR assessed by IRC	The proportion of subjects achieving a best overall response of CR, CRi, nPR, or PR per IRC assessment at or prior to initiation of subsequent antineoplastic therapy.	Chi-square test.
Overall survival (OS)	Time from the date of randomization to the date of death from any cause. All deaths observed at the time of the analysis will be considered as events. For subjects who were not known to have died at the time of the analysis, OS data will be censored at date last known alive.	Analyzed the same as PFS primary analysis.
Rate of MRD-negative response	Proportion of subjects who achieved MRD-negative response defined as < 1 CLL cell per 10,000 leukocytes as assessed by flow cytometry of a bone marrow aspirate or peripheral blood sample per central laboratory.	Chi-square test for MRD-negative response rate by bone marrow

- Rate of infusion related reactions will be analyzed using a Chi-square method.
- Rate of sustained platelet improvement will be analyzed using a Chi-square method
- Rate of clinically meaningful improvement in EQ-5D-5L utility score will be analyzed using a Chi-square method

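### Region defines the randomisation schemes but is left out of the stratified time-to-event tests; adding it as a covariate is a cheap improvement to a test that is already valid

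*SAP*

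**What the plan says.** **Randomisation.** SAP section 1.7.2: "Two randomization schemes will be generated: one for each geographic region (North America versus Rest of World". ECOG (two levels) and cytogenetics (three levels) are then applied under each scheme, with 1:1 allocation in each stratum through the IWRS. Protocol sections 3.1, 5.1 and 10.2 describe the same arrangement.

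**Analysis.** SAP section 4: "The following two randomization stratification factors will be used for the stratified analysis/test: ECOG performance status (0, 1 versus 2) and Cytogenetics". It gives this purpose: "To reflect the randomization process and maintain the integrity of randomization, all stratified tests will be based on randomization stratification factors". Region is not mentioned.

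**Primary test.** SAP section 1.3: "These hypotheses will be tested using a 2-sided stratified log-rank test at α level of 0.05". SAP Table 1 and protocol section 10.7.1 name a log-rank test and a Cox model without saying that either is stratified. By Table 1, OS and PFS in the high-risk set are analysed in the same way as the primary endpoint. The binary endpoints use a plain chi-square test with no stratification.

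**Sizing.** SAP section 1.4: "94 PFS events provide 80% power to achieve a statistical significance level of 5% (2-sided) under exponential distribution", for a hazard ratio of 0.55, a control median of 27 months and equal allocation.

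**The concern.** Allocation is balanced within region by ECOG by cytogenetics, which makes 2 × 2 × 3 = 12 cells. The analysis conditions on 2 × 3 = 6. Region therefore acts as a third stratification factor in the design and is absent from the analysis, against the SAP's stated purpose.

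If region is prognostic, leaving it out has two effects. The treatment contrast is already balanced by region, but the log-rank variance does not take credit for that balance, so the test becomes conservative. Heterogeneity left within strata also dilutes the estimated effect, so power falls. PFS is the first gate in the serial testing order of SAP section 1.6, so lost power there affects everything below it.

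The point concerns the time-to-event tests only. The chi-square endpoints use no stratification factor at all, so region is not the particular gap there.

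**Working it through.** **1. The plan's own figures.** Inputs from SAP section 1.4: HR 0.55, two-sided 5%, 80% power, 1:1, 212 subjects at 18 per month, about 36 months.

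- Freedman events: (1.960 + 0.842)² × (1.55/0.45)² = 7.85 × 11.86 = 93.1, rounded up to **94**, an exact match. Power at 94 events: Φ(√94 × 0.45/1.55 − 1.960) = Φ(0.855) = 80.4%.
- Schoenfeld events: 4 × 7.85/(ln 0.55)² = 87.8, so 88. Power at 94 events: Φ(√94 × 0.598/2 − 1.960) = Φ(0.938) = 82.6%.
- Arm A median: 27/0.55 = 49.1 months. Expected events at month 36, with accrual over 212/18 = 11.8 months: 106 × (0.5366 + 0.3456) = 93.5.

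These formulas contain no strata, so the treatment of region does not alter them.

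**2. Three tests compared by simulation.** 212 subjects at 18 per month, cut at the 94th event, control median about 27 months, permuted blocks of 4 in the 12 cells, 8,000 trials per setting. Protocol section 1.1.3 puts del 17p at about 10%. The other inputs are assumptions: hazard ratios of 2.0 for del 17p, 1.5 for del 11q (18% of subjects) and 1.5 for ECOG 2 (8%), a multiplier of 0.85 for other cytogenetics, and no dropout. The region effect and split are also assumed. The Monte Carlo SE for power is √(0.8 × 0.2/8000) = 0.45 points; the paired SE is for the difference in the same trials.

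Power at HR 0.55:

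| Region HR (split) | SAP, 6 strata | 12 strata | 6 strata + region covariate | Covariate minus SAP (paired SE) |
|---|---|---|---|---|
| 1.0 (50/50) | 81.3% | 80.4% | 81.5% | +0.2 (0.1) |
| 1.5 (50/50) | 80.7% | 80.5% | 81.5% | +0.8 (0.15) |
| 2.0 (50/50) | 78.8% | 79.9% | 80.9% | +2.1 (0.2) |
| 3.0 (50/50) | 76.0% | 80.4% | 81.0% | +5.0 (0.3) |
| 1.5 (25/75) | 80.3% | 80.0% | 80.7% | +0.4 (0.15) |

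Across four runs of 3,000 to 8,000 trials per setting, some with slightly different prognostic inputs, the gain at a 50/50 split was 0.1 to 0.4, 0.6 to 0.8, 1.9 to 2.5 and 4.7 to 5.4 points for region HR 1.0, 1.5, 2.0 and 3.0.

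**3. Type I error, two-sided, SAP test v region covariate.** At a 50/50 split: 5.1 v 5.1%, 4.9 v 5.2%, 4.5 v 5.0% and 3.5 v 4.9% for region HR 1.0, 1.5, 2.0 and 3.0. The SE is √(0.05 × 0.95/8000) = 0.24 points. At 25/75 with region HR 1.5: 5.6 v 5.7%. The two tests are equally far from 5% there, so omitting region is not the cause. Over all runs the SAP test's size was 4.0 to 4.8% at region HR 2.0 and 3.5 to 3.7% at 3.0.

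**4. Why not 12 strata.** In a further simulation (del 11q 15%, hazard multipliers 2.5, 1.4 and 0.85 by cytogenetic group), about 10.6 cells were occupied and about 4.7 of them held fewer than 5 events. Information fell from about 90 to 88 event-equivalents. With no region effect, power went from 81.1% with 6 strata to 80.3% with 12, a loss of 0.8 points (14,000 trials, paired SE 0.16).

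**5. OS and high-risk PFS.** At the 33 deaths and HR 0.39 of protocol section 10.7.2.3, the covariate gained 0.1, 0.2, 0.5 and 1.5 points of power for region HR 1.0, 1.5, 2.0 and 3.0. High-risk PFS was not evaluated; the documents give no event count for that set.

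**The case against.** The strongest defence is that the SAP follows its own labels. Only ECOG and cytogenetics are called stratification factors; region defines the scheme. Pooling over a balanced scheme-level factor to avoid sparse strata is a legitimate prespecified choice, and the planned test is valid. This stands, with two limits: the SAP does not give that reason, and sparseness is an argument against 12 strata, not against one covariate.

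Second, a region hazard ratio of 2 to 3 would make geography at least as prognostic as the value of 2.0 assumed here for del 17p, which protocol section 1.1.3 treats as the leading adverse factor. A blinded IRC with central radiology and hematology also limits regional differences in how progression is read. This stands too: a gain under 1 point is the safer expectation.

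Third, an additive covariate does not reproduce the 12 cells, and it replaces the protocol's log-rank with a model-based score test that assumes proportional regional hazards. That is a fair cost. A plan that kept the present test and added the region-adjusted one as a sensitivity analysis would also be defensible.

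A reader might infer that the primary test has the wrong size in a harmful sense, or that the trial is underpowered. Neither follows. The simulated departures attributable to omitting region are all in the conservative direction, and the event target reproduces exactly.

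**Conclusion.** The mismatch between design and analysis is plain from the text, and it is minor. The six-stratum log-rank is valid, and clearly conservative only when region is very strongly prognostic. Region as a covariate within the six strata showed no power loss in any setting tried. Its PFS gain is about 0 to 1 point for a region HR of 1.0 to 1.5, about 2 points at 2.0 and about 5 points at 3.0.

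It is tempting to call this a substantial free gain in power for every stratified endpoint. The documents do not support that: they contain no regional prognostic effect and no regional split. The OS gain is smaller than the PFS gain, and the high-risk PFS gain is unknown. All sizes depend on the assumed prognostic effects, block size and absence of dropout.

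**What to change.** Before database lock, amend SAP section 4 so that:

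- the ECOG by cytogenetics strata stay as they are;
- region, as recorded in the IWRS, enters the stratified Cox model as a covariate, and the score test for treatment from that model is the primary PFS test, with the hazard ratio from the same model;
- the present six-stratum log-rank is reported as a sensitivity analysis;
- region is not crossed with the other factors into 12 strata;
- OS and high-risk PFS follow the same method, as Table 1 already has them inherit it.

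Align the wording of SAP section 1.3, SAP Table 1 and protocol section 10.7.1, and say in Table 1 that the log-rank and Cox analyses are stratified. If the sponsor prefers to keep the present primary test, the SAP should give the reason for pooling over region and prespecify the region-adjusted analysis as a sensitivity analysis.

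The cost is one variable that the randomisation system already uses and matching edits in those places. Sample size and event target do not change. The statistical price is a covariate-adjusted score test, with its assumption of proportional regional hazards, in place of a plain stratified log-rank.
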